## CLINICAL PROTOCOL

SPONSOR: ZMS

PROTOCOL: ZMS-1500-Pa2023

## CLINICAL PROTOCOL

SPONSOR: ZMS

PROTOCOL: ZMS-1500-Pa2023

### PROTOCOL AMENDMENT HISTORY

Version Number	Description of Change(s)	Reason for Change
1.0	Initial protocol; no changes	N/A

[This space is intentionally left blank]

## CLINICAL PROTOCOL

SPONSOR: ZMS

PROTOCOL: ZMS-1500-Pa2023

## CLINICAL PROTOCOL

SPONSOR: ZMS

PROTOCOL: ZMS-1500-Pa2023

## CLINICAL PROTOCOL

SPONSOR: ZMS

PROTOCOL: ZMS-1500-Pa2023

### 1 INTRODUCTION

Intraoperative and postoperative hemorrhage incidence can vary depending on the type of surgery and can lead to severe clinical complications ranging from mild anemia to fatal hemorrhagic shock. Those that recover from severe hemorrhagic events often have poor functional outcomes and are at risk for greater long-term mortality. Numerous studies reveal that post-operative hemorrhagic events are also quite frequent, occurring in as many as 13 to 19% of patients following various type of surgeries (i.e., major pancreatic resections, transoral robotic surgery (TORS) for oropharyngeal squamous cell carcinoma, and living-donor transplants). Hemorrhagic shock is also a leading cause of death in trauma.

Monitoring and detecting fluid changes in patients can be complicated. Physiological responses associated with hemorrhagic events are often delayed because of compensation mechanisms that act to sustain blood pressure and protect tissue perfusion. The ability to continuously and non-invasively detect changes in central blood volume and blood loss will permit appropriate hemodynamic management during events at high risk for acute blood loss such as surgery, trauma, post-operative care and other therapeutic procedures. Through early detection and improved hemodynamic monitoring, optimization of fluid balance, anesthesia titration, and augmenting other acute care management requirements, a clinician should be able to improve overall patient stability, minimize complications, diminish surgical trauma and reduce recovery time.

Current methods for acutely monitoring blood volume and blood loss include monitoring of vital signs (such as heart rate, blood pressure, respirations, and oxygen saturation), invasive central venous (right heart central venous pressure measurement and Swan-Ganz pulmonary capillary wedge pressure measurements) and arterial catheters designed to monitor hemodynamic status centrally. Vital sign monitoring may not indicate small amounts of acute blood loss and arterial and venous cannulations can create insertion complications such as perforations in the vasculature, pneumothorax, arrhythmias, thrombosis and infection. While invasive central monitoring may provide extremely accurate information, changes may not be good indicators of early central hypovolemia or with smaller blood volume reductions. New non-invasive technologies have recently become available but often include many physiological parameters that may require expedited clinical interpretation in high stress environments and have not become well-established.

The Zynex Cardiac Monitor, Model 1500 (CM-1500) uses a relative patient standard approach by non-invasively and simultaneously monitoring five (5) physiological parameters, including bioelectrical impedance, electrocardiogram (ECG) amplitude, photoplethysmogram (PPG) amplitude, heart rate (HR), and skin temperature. The CM-1500 starts by creating a baseline for each patient in a normal state. When the monitoring session starts, each patient starts with a Relative Index (RI) of 100, signifying the collection of parameters near their original baseline value(s). The Relative Index value acts as a combinational score for all the parameters indicative of relative fluid change.

#### 1.1 CLINICAL RATIONALE

The proposed clinical study is designed to examine whether subject positioning has an effect on how the CM-1500 individual parameters and Relative Index change in response to small blood volume changes in

# CLINICAL PROTOCOL

SPONSOR: ZMS

PROTOCOL: ZMS-1500-Pa2023

healthy individuals consented to undergo a 1-unit blood draw (approx. 500mL). An initial feasibility study was conducted (n = 12 subjects) to confirm that the CM-1500 can be used to track acute blood loss in healthy individuals donating 500mL of blood in the supine position. Additional studies are being conducted in various healthy volunteer and clinical settings to characterize RI performance when known volumes of fluid are removed.

## 2 INVESTIGATIONAL PLAN

### 2.1 OBJECTIVES

The primary objective of the study is to examine the effects of subject positioning on the ability of the CM-1500 parameters to detect minor blood loss.

Exploratory objectives of the study will include:

- Compare the performance of the CM-1500 monitoring during a whole blood donation with subjects positioned in either a fully supine position (180°) or in a reclined position (approx. 135°)
- Investigate any possible correlations between adverse events, subject demographics, changes in the individual parameters, and timing of when the events occurred.

### 2.2 STUDY DURATION

Enrollment in the study is expected to take approximately five (5) months, and data analysis may take up to an additional two (2) months to complete.

### 2.3 STUDY DESIGN

The study is a prospective, non-randomized, non-blinded, non-significant risk study enrolling up to 60 healthy adult subjects consented to undergo a 1-unit whole blood draw procedure.

The present study will involve enrolling subjects that will undergo blood draw wearing the study device (CM-1500) and capture study-required physiological parameters pre-, during, and post-donation.

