### 4 SUBJECT POPULATION AND SELECTION

#### 4.1 POPULATION AND ANTICIPATED NUMBER OF SUBJECTS

Up to 60 healthy adult subjects who meet the inclusion and exclusion criteria will be enrolled in the study. A minimum of 20 subjects will be enrolled at each of the subject positionings (180° and 135°). Every reasonable effort will be made to achieve a 50:50 split between the two subject positionings.

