### 5.2 DEMOGRAPHIC AND BASELINE DATA

Demographic and enrollment data collection will include capturing health screening data on a case report form (CRF). These data will include but are not limited to skin tone, smoking history, a blood donation anxiety questionnaire, blood donation history, and if subjects are currently taking any medications or supplements that could impact their physiological response to the blood draw procedure. Female subjects will self-report they are not currently pregnant or have been pregnant in the previous six (6) weeks.

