## CLINICAL PROTOCOL

SPONSOR: ZMS

PROTOCOL: ZMS-1500-Pa2023

Baseline hemoglobin will be collected as part of a standard blood draw procedure via a finger stick (or per standard of care for the site). Subjects that are unable to proceed with the blood donation due to their baseline hemoglobin level will be consent ineligible.

Following demographic and enrollment data collection and PRIOR to blood donation, all subjects will be connected to the CM-1500 per the Instructions for Use. Designated study personnel must ensure that the subject ID number and gender is entered for each subject prior to starting a new monitoring session.

The CM-1500 will be connected to the subject's left side of the body. Once the needle stick has been completed but the line is clamped to prevent premature blood draw, the subject's chair should be adjusted to the position assigned upon enrollment. The monitoring session should then start with the subject placed in the designated position for a minimum of ten (10) minutes before the baseline measurements will be recorded. Just prior to the blood draw, a skin temperature recording should occur on the left dorsal wrist.

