### 5.3 SUBJECT PARTICIPATION

Subjects will proceed with the blood draw procedure wearing the CM-1500 on the left arm. For this protocol, blood draws can only occur on the right arm. Subjects will remain in their assigned position for the entirety of the procedure unless position change is required in response to a subject reaction. Immediately prior to the start of the blood donation procedure, the Investigator or designated study personnel will press the 'MARK EVENT' button on the CM-1500 and record the local time on the CRF which will signify the start of the procedure on the device.

The Investigator or designated study personnel will monitor the subject per standard of care throughout the procedure and record any adverse events noted. Total amount of blood collected will vary per subject based upon their estimated blood volume, and the final amount drawn will be recorded.

Immediately following completion of the blood donation, the Investigator or designated study personnel should press 'MARK EVENT' on the CM-1500 and record the local time on the CRF. Skin temperature from the left dorsal wrist should again be measured at this time.

Subjects will remain connected to the CM-1500 for at least ten (10) minutes following the donation procedure. Following the 10-minute post-donation monitoring period, subjects will be disconnected from the study device, and study participation will be complete.

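### Position is the subject of the primary objective, but each subject gets one position without randomization or a stated assignment rule, so a 180° versus 135° difference is open to confounding

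*Combined protocol and SAP*

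**What the plan says.** Section 2.1 opens: "The primary objective of the study is to examine the effects of subject positioning". The explicit contrast of the two positions comes under the exploratory objectives: "Compare the performance of the CM-1500 monitoring during a whole blood donation with subjects positioned in either a fully supine position" (180°) or reclined (about 135°).

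Section 2.3 describes the design: "The study is a prospective, non-randomized, non-blinded, non-significant risk study enrolling up to 60 healthy adult subjects".

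Assignment is mentioned in three places:

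- Section 4.1 controls numbers: "A minimum of 20 subjects will be enrolled at each of the subject positionings", and "Every reasonable effort will be made to achieve a 50:50 split between the two subject positionings".
- Section 5.2 gives the timing. After the needle stick, the "chair should be adjusted to the position assigned upon enrollment".
- Section 5.3 fixes one position per subject: "Subjects will remain in their assigned position for the entirety of the procedure unless position change is required in response to a subject reaction".

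The available text gives no rule (sequence, alternation, date, chair, staff or subject choice) for who receives which position. Section 9.3.3 summarizes baseline variables without mentioning position. Section 9.1 calls this a feasibility study without statistical hypotheses and bases its size on clinical judgment.

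**The concern.** With one position per subject, an effect of position can be learned only by comparing different people. Without randomization, those people may differ in ways that also affect the outcome.

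The endpoints in section 2.4 are before-to-after changes, and section 3.1.3 starts the Relative Index (RI) at 100 for everyone. Stable differences in level therefore drop out, but differences in response to the draw do not. The protocol itself points to such differences. Section 5.2 records "medications or supplements that could impact their physiological response to the blood draw procedure", and section 5.3 says the volume drawn depends on estimated blood volume.

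Calendar time is a second route. Section 2.2 expects about five months of enrollment, and nothing requires the two positions to be interleaved over that period. If one were largely filled first, any drift in staff technique, donor mix or conditions would appear as a position effect.

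At stake is the contrast the study exists to examine. Later analysis can adjust for recorded factors, but not fully for unrecorded ones.

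**Working it through.** The plan has no figure to reproduce: it gives no effect size, SD or power. The calculations below show scale only. **All bias, effect and drift values are assumed, and the between-position test is not in the plan.**

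**Inputs from the protocol.** Up to 60 subjects, at least 20 per position, 50:50 target (4.1); two-sided 5% level (9.3.4). Three splits are allowed: 30/30, 20/20 and, if the 50:50 effort fails, 20/40.

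**Step 1: effect of a bias of b SD when position has no effect.** In units of the SD of the change, SE = √(1/n₁ + 1/n₂). The 95% CI half-width is t(0.975, n₁+n₂−2) × SE. The rejection rate is that of a two-sample t-test with noncentrality b/SE.

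| Split | SE | Half-width | b=0.05 | b=0.1 | b=0.2 | b=0.3 | b=0.4 |
|---|---|---|---|---|---|---|---|
| 30/30 | 0.2582 | 0.5168 | 5.42% | 6.68% | 11.87% | 20.79% | 33.15% |
| 20/20 | 0.3162 | 0.6402 | 5.27% | 6.10% | 9.46% | 15.23% | 23.43% |
| 20/40 | 0.2739 | 0.5482 | 5.37% | 6.49% | 11.09% | 18.99% | 30.06% |

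As a share of the half-width, these biases run from 0.05/0.5168 = 9.7% to 0.4/0.5168 = 77.4% at 30/30, and from 7.8% to 62.5% at 20/20. With no bias the rate is 5% at any split, so equal counts alone do not protect the comparison.

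**Step 2: what could produce such a b.** For one binary factor at 30/30, b = effect on the change × (difference in counts / 30).

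- Effect 0.25 SD, gap of 3: 0.25 × 3/30 = 0.025 SD; rejection 5.1%.
- Effect 0.5 SD, gap of 6 (for example 9 versus 3 taking a relevant medication): 0.5 × 6/30 = 0.10 SD; 6.7%.
- Effect 0.8 SD, gap of 9: 0.8 × 9/30 = 0.24 SD; 15.0%.

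**Step 3: calendar drift.** Let the change drift linearly by D SD over 60 enrollments, at times i/59 for i = 0 to 59.

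- One position filled first: the mean positions are 14.5 and 44.5, so the bias is 30/59 × D = 0.508 × D.
- Strict alternation: 1/59 × D = 0.017 × D.
- Permuted blocks of 4 and 6 (20,000 simulated lists): mean 0.000, SD 0.017 × D, and 99% of lists within 0.045 × D. Group counts never differed by more than 2.

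**Step 4: what randomization does not do.** With 12 carriers of a binary factor among 60 subjects split 30/30, the hypergeometric probability of a gap of 6 or more between positions is 10.4%. Randomization removes expected bias, and chance imbalance remains.

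**The case against.** The strongest reply is that the design is openly declared and its purpose limited. Section 2.3 says it is not randomized, section 9.1 calls it hypothesis-generating, the direct position contrast is exploratory, and section 9.3.4 plans only before/after tests against zero. On that view there is no internal error, and the rejection rates describe a test nobody has planned.

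Part of this stands. The percentages are illustrations, and the missing between-position analysis is a separate gap that adds no weight here. The upper figures also lack a worked mechanism: 0.4 SD from one binary factor at 30/30 would need a gap of 24 subjects at a 0.5 SD effect, or 15 at 0.8 SD. The 9-versus-3 example is an imbalance that chance can still produce after randomization. But the feasibility label explains the absence of a power calculation; it does not make an avoidable bias harmless. Even a descriptive comparison of positions carries it.

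Timing narrows the risk. Position is assigned at enrollment, which section 5.1 places at consent, apparently before medication, anxiety and hemoglobin data are collected. Selection on visible traits, on preference or by calendar time remains possible, though nothing in the documents shows that it will occur.

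The content of Figure 1 was not available and might hold a rule such as alternation. That would greatly reduce drift bias, but the study would still be non-randomized. The exploratory look at correlations with demographics in section 2.1 is not an adjustment of the position comparison.

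**Conclusion.** The point holds. As written, the plan cannot separate the effect of position from who was placed in each position and when. It should be fixed because the remedy is cheap and needs no extra subjects.

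The actual bias is unknown. It is negligible at the low end of the assumed range (5.4% rejection at 0.05 SD, 30/30) and substantial at the high end (33.2% at 0.4 SD), with single-factor examples at 5.1% to 15.0%. These figures assume a t-test on change scores with a common SD and no true position effect. The before/after results within each position are unaffected. The design facts are firm; the statement that no assignment rule exists is limited to the available text.

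**What to change.** Preferred change:

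- **2.3:** describe the study as randomized with respect to position.
- **4.1 and 5.2:** allocate position 1:1 from a concealed permuted-block list, for example with blocks of 4 and 6, keeping N at up to 60. Open each allocation after eligibility, including hemoglobin, is confirmed and as near to chair adjustment as is practical.
- **4.4:** a replacement subject takes the next entry on the list.
- **9.2:** the comparison of positions includes all allocated subjects by assigned position, including those whose position changed after a reaction. Count subjects connected but never allocated separately, and list by position any allocated subject without a post-draw value.

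If an operational constraint rules this out, state the constraint and the assignment rule, interleave the positions over the five months, and tabulate baseline data by position in 9.3.3. Adjust the comparison for a short list of factors, fixed in advance and recorded before positioning. Candidates are sex, medications, the anxiety questionnaire, donation history and hemoglobin, plus a body-size measure if one is recorded by then. With 40 to 60 subjects the list must be kept small. Do not adjust for volume drawn, which is determined after positioning. Report the result as an association.

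The cost is an IRB-approved amendment, an allocation list with envelopes, and one more step during set-up, possibly close to the needle stick. Flexibility in choosing position is lost. No subjects or visits are added. The documents give no reason for non-random assignment, so a practical obstacle cannot be excluded.

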### 2.4 STUDY ENDPOINTS

The study endpoints include the change and percentage of change between measurements before and after blood draw in the Relative Index, individual parameters and standard physiological parameters. The change is defined as the value after draw minus the one before draw. The percentage of change is the change value divided by the value before draw. Other endpoints such as area under receiver operating characteristic (ROC) together with sensitivity and specificity at various thresholds are also derived for the Relative Index, individual parameters and each of standard physiological parameters in detecting in detecting minor blood loss (i.e., ~500mL).

## CLINICAL PROTOCOL

SPONSOR: ZMS

PROTOCOL: ZMS-1500-Pa2023

### 3 STUDY DEVICE

#### 3.1 CARDIAC MONITOR, MODEL 1500 (CM-1500)

##### 3.1.1 DEVICE DESCRIPTION

The CM-1500 is a U.S. Food and Drug Administration (FDA) cleared non-invasive monitoring device that simultaneously monitors five (5) parameters of a patient's body. Parameters include bioelectrical impedance, heart rate, ECG amplitude, PPG amplitude, and skin temperature. A combination of these parameters is represented by a single number known as the Relative Index value. This value is indicative of relative changes in fluid volume. The Relative Index (RI) is a unique functionality of the Zynex Cardiac Monitoring Device.

##### 3.1.2 DEVICE DESIGN AND COMPONENTS

The CM-1500 is an all-inclusive device that includes the following components: display monitor (1), power supply (1), trunk cable (1), wrist cuff with attached PPG finger glove (1), wrist strap (1), and electrode array set (2). The wrist cuff with attached PPG finger glove may be cleaned and reused. The wrist strap is single-subject use. The electrode array sets are single-use, single-subject.

##### 3.1.3 PRINCIPLES OF OPERATION

The CM-1500 measures bioelectrical impedance (ohms), heart rate (BPM), ECG amplitude (mV), PPG amplitude, and skin temperature (°C or °F). As parameters change towards indications of fluid change/imbalance, the Relative Index, which acts as a combinational score of percent change values for all of the parameters, will compound these changes into a singular value to signify overall fluid changes/imbalances within the patient's body. When the monitoring session starts, every patient will start with a Relative Index of 100, signifying the combination of physiological parameters is near or at their original baseline values for all five monitored parameters. All parameters are continuously measured and tracked during a monitoring session. ECG and PPG amplitude values are only visible on the Advanced monitoring session display mode, as selected in the Setup screen.

##### 3.1.4 INDICATIONS FOR USE

Per the device's FDA clearance, the CM-1500 is indicated for monitoring bioelectrical impedance, heart rate, ECG amplitude, and PPG amplitude and their relative changes, indicative of relative changes in fluid volume in adult patients.

##### 3.1.5 INTENDED USE

Per the device's FDA clearance, the CM-1500 is intended to be used in professional medical environments, i.e., hospitals, clinics, and research institutions. The CM-1500 is a standalone device intended for desktop use, where device operation is to be performed as uninterrupted patient monitoring. The CM-1500 shall only be used by a qualified device operator. The operator shall have knowledge of the system and data interpretation obtained via medical education, system documentation, and specific courses. The device does not report any diagnosis but provides numerical values; it is ultimately the physician's responsibility to make proper diagnosis and judgments based on these values.

## CLINICAL PROTOCOL

SPONSOR: ZMS

PROTOCOL: ZMS-1500-Pa2023

### 4 SUBJECT POPULATION AND SELECTION

#### 4.1 POPULATION AND ANTICIPATED NUMBER OF SUBJECTS

Up to 60 healthy adult subjects who meet the inclusion and exclusion criteria will be enrolled in the study. A minimum of 20 subjects will be enrolled at each of the subject positionings (180° and 135°). Every reasonable effort will be made to achieve a 50:50 split between the two subject positionings.

#### 4.2 SUBJECT INCLUSION CRITERIA

- I.1 Ability to provide written informed consent
- I.2 Ability and willingness to comply with the study procedures and duration requirements
- I.3 18 years of age or older
- I.4 Consented and eligible to undergo a single unit whole blood donation

#### 4.3 SUBJECT EXCLUSION CRITERIA

- E.1 Females who are pregnant or breastfeeding
- E.2 Undergone an amputation of any upper extremity
- E.3 Diagnosed with dextrocardia
- E.4 Subjects who have a pacemaker
- E.5 Subjects with body hair density which prevents adequate application of device electrodes

#### 4.4 SUBJECT WITHDRAW / EARLY TERMINATION

Subjects who withdraw from the study before using the CM-1500 will be replaced. The reason the subject withdrew from the study may be recorded; subjects are not required to provide a reason. Subject withdrawal / early termination criteria may include but are not limited to:

- W.1 Subject requests to be withdrawn from the study or withdraws consent.
- W.2 Subject refuses to comply with required study procedures.
- W.3 An Adverse Event ("AE") makes the continuation of the subject impossible or inadvisable
- W.4 The Investigator determines it is in the subject's best interest to discontinue from the study.

[figure not shown]
